### 5.7.2. Clinical Laboratory Measurements

Laboratory measurements include clinical chemistry, hematology and urinalysis results, and will be converted to values in standard international units. Summaries of laboratory variables will include:

- Descriptive statistics of laboratory result and change from baseline by visit.
- The number (n) and percentage (%) of subjects with treatment-emergent PCSVs. This summary will be provided based on all patients in the SAF as well as in the subgroup of SAF patients who did not meet the PCSV criterion at baseline.
- Shift tables based on baseline normal/abnormal and other tabular and graphical methods may be used to present the results for parameters of interest

### **5.7.3. Analysis of Vital Signs**

Summaries of vital sign variables will include:

- Descriptive statistics of vital sign variable and change from baseline by visit
- The number (n) and percentage (%) of subjects with treatment-emergent PCSV
- Shift tables based on baseline normal/abnormal and other tabular and graphical methods may be used to present the results for parameters of interest

### **5.7.4. Analysis of 12-Lead ECG**

Summaries of 12-lead ECG parameters will include:

- Descriptive statistics for each ECG parameter and change from baseline
- The number (n) and percentage (%) of subjects with PCSV
- ECG status (i.e. normal, abnormal) summarized by a shift table

### **5.7.5. Physical Exams**

Abnormal status will be tabulated for assessments of each physical exam category and presented by visit.

## **5.8. Analysis of Pharmacokinetic Data**

The following analyses will be conducted:

- Descriptive statistics of functional dupilumab concentrations in serum at each sampling time by treatment group
- Graphical presentations of median and mean (+/- SD) functional dupilumab concentration in serum vs nominal time
- Graphical presentations of individual functional dupilumab concentration in serum vs actual sampling time
- Assessment of the impact of anti-drug antibodies on functional dupilumab concentrations in serum.

No formal statistical analysis will be performed.

## **5.9. Analysis of Immunogenicity Data**

### **5.9.1. Analysis of ADA**

The immunogenicity variables mentioned in Section 4.7 will be summarized using descriptive statistics. Immunogenicity will be characterized by ADA responses as defined in Section 4.7 and titers observed in patients in the ADA analysis set.

The following listings will be provided:

- Number (n) and percent (%) of ADA-negative patients that are negative in the ADA assay at all time points by treatment groups

- Number (n) and percent (%) of patients with Pre-existing immunoreactivity by treatment groups
- Number (n) and percent (%) of treatment-emergent ADA positive patients by treatment groups and ADA titer categories
  - Number (n) and percent (%) of persistent treatment-emergent ADA positive patients
  - Number (n) and percent (%) of indeterminate treatment-emergent ADA positive patients
  - Number (n) and percent (%) of transient treatment-emergent ADA positive patients
- Number (n) and percent (%) of treatment-boosted ADA positive patients by treatment groups and ADA titer categories

**Titer categories (Maximum titer values)**

- Low (titer <1,000)
- Moderate (1,000 ≤ titer ≤ 10,000)
- High (titer >10,000)

**5.9.2. Analysis of Neutralizing Antibody (NAb) Data**

Samples positive in the dupilumab ADA assay will be further characterized for the presence of NAb to dupilumab. The absolute occurrence (n) and percent of patients (%) with NAb status will be provided for patients in the NAb analysis set by treatment groups.

**5.10. Association of Immunogenicity with Exposure, Safety and Efficacy**

The analyses in this section will only be performed if incidence of treatment emergent ADA positive is sufficient to make meaningful conclusions (i.e. more than 5% in any treatment group).

**5.10.1. Association of immunogenicity with exposure**

Potential association between ADA responses and systemic exposure to dupilumab will be explored by treatment groups. Plots of dupilumab concentration may be provided for analyzing the potential impact of ADA response status, titer and NAb on individual patient drug concentration profile.

**5.10.2. Immunogenicity and Safety/Efficacy**

Potential association between ADA responses and safety may be explored with a primary focus on the following safety events during the TEAE period:

- TEAE
- Serious TEAE
- TEAE leading to permanent treatment discontinuation

- Injection site reaction (HLT=' Injection site reaction')
- Hypersensitivity (AESI category 'Hypersensitivity')
- Anaphylaxis (SMQ: Anaphylactic Reaction [Narrow])

Potential association between ADA responses and impact on individual patient efficacy endpoint profiles may be explored (e.g. scatter plot or spaghetti plot).

The safety and efficacy analyses mentioned above will be conducted using the following ADA response categories:

- ADA negative patients, that is patients with pre-existing immunoreactivity or negative in the ADA assay at all time points.
- ADA positive patients, that is patients with treatment-emergent or treatment-boosted response.
- Patients with persistent treatment-emergent ADA response
- NAb positive patients, that is ADA positive patients who were positive in the NAb assay at any time point analyzed.
- Maximum post-first dose titer in treatment-emergent or treatment-boosted ADA positive patients:
  - Low (titer <1,000)
  - Moderate ( $1,000 \leq \text{titer} \leq 10,000$ )
  - High (titer >10,000)

## 5.11. Analysis of Biomarker Data

Descriptive statistics for the observed values, change from baseline and percent change from baseline values by treatment and visit will be provided for the biomarker variables as described in Section 4.8.

The Wilcoxon signed-rank test will be used to test if the change or percentage change from baseline value is significantly different from zero. Nominal p-value will be reported.

For Part B, exploratory analyses for the difference between the dupilumab groups and the placebo group in the change and percent change from baseline values will be performed using a rank-based ANCOVA model, with treatment group and randomization stratification factors as fixed factors, and the relevant baseline value as a covariate. Missing value will be imputed by LOCF method using available post-baseline data for visits up to week 24. P-value for differences from placebo will be provided.

Correlation of baseline TARC (measured value), Eotaxin-3, and IgE (measured value) with the following clinical endpoints will be explored using ANCOVA model. The model will include the below clinical endpoint as the dependent variable, with randomization stratification factors, the log10 transformed baseline biomarker value, treatment group, and treatment by baseline biomarker interaction as the predictor variables. Model coefficients and P-value will be provided to indicate significance of the correlation/association.

- Change from baseline to week 24 in DSQ total score
- Percent change in peak esophageal intraepithelial eosinophil count (eos/hpf) from baseline to week 24
- Absolute change in EoE EREFS total score from baseline to week 24
- Absolute change in EoEHSS mean grade score from baseline to week 24
- Absolute change in EoEHSS mean stage score from baseline to week 24

Correlation of baseline TARC (measured value), Eotaxin-3, IgE (measured value), and positivity to at least one antigen-specific IgE (The threshold for positivity being  $\geq 0.35$  kU/L) with the histologic responder (histologic response of esophageal intraepithelial eosinophil count of  $\leq 6$  eos/hpf at week 24) will be explored using the logistic model. The model will include the histologic responder/non-responder as the dependent variable, with randomization stratification factors, the log10 transformed baseline biomarker data, treatment group, and treatment by baseline biomarker interaction as the predictor variables. Model coefficients and P-value will be provided to indicate significance of the correlation/association.

Association of the DSQ score with the histology measures and EREFS score will be explored. Specifically, Pearson's correlation coefficient will be provided for the correlation of the following pairs within each treatment group:

- Total EoEHSS grade and stage scores (excluding lamina propria) vs. DSQ score at week 24
- Peak eos count vs. DSQ score at week 24
- Total EREFS score vs. DSQ score at week 24
- Change from baseline in total EoEHSS grade and stage scores (excluding lamina propria) vs. change from baseline in DSQ score at week 24
- Change from baseline in peak eos count vs. change from baseline in DSQ score at week 24
- Change from baseline in total EREFS score vs. change from baseline in DSQ score at week 24

All the above correlation/association analyses will be performed on the FAS for

- All observed data, regardless of the use of rescue treatment
- Observed data, with data set to missing for all time points subsequent to the use of rescue treatment

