8.2.6. Pharmacodynamic and Exploratory Biomarker Procedures

In this study, research assessments will be performed to explore EoE, how dupilumab may modify the underlying disease process in EoE, type 2 inflammation, and predictors of dupilumab safety and efficacy.

Samples for eotaxin-3 (heparinized plasma); serum TARC, total IgE, and allergen-specific IgE and IgG4s will be collected at time points according to Table 1 and Table 2. The biomarkers studied are believed to be relevant to the pathophysiology of EoE, response to treatment (ie, assessment of type 2 inflammation) and baseline predictors of response and dupilumab mechanism of action.

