#### DSQ total score (continuous endpoint)

The absolute change from baseline in the DSQ total score at week 24 will be analyzed using an analysis of covariance (ANCOVA) model for the FAS with treatment group, randomization stratification factors, and relevant baseline measurement as covariates included in the model. The cumulative distribution function (CDF) of the absolute change from baseline in the DSQ total score at week 24 will be graphed to present the between-treatment-group differences at each level of the change.

Data may be collected after the patient discontinued treatment and will be included in the analyses.

To account for use of rescue treatment (see Section 0), data will be set to missing for all time points subsequent to the use of rescue treatment in the primary analysis.

For patient with missing value or data set to missing after rescue for the DSQ total score at week 24, their data for Week 24 will be imputed by MI based on patients who remained in the trial with observed values relevant to analysis. To account for the uncertainty in the imputation, missing data at week 24 will be imputed 50 times to generate 50 complete datasets by using the MI procedure in Statistical Analysis Software (SAS).

MI will follow the 2 steps below using a random seed number of 6681774 in both steps:

1. Step 1: Use the Markov Chain Monte Carlo (MCMC) method to fill in intermittent missing values (ie, those missing values followed by observed values at subsequent visits) so that a monotone missing pattern will be formed.
2. Step 2: Using the datasets from step 1, missing data through week 24 will be imputed using the regression method with treatment group, randomization stratification, relevant baseline measurement, and post-baseline measurement up to week 24 included in the regression model.

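### The exploratory biomarker models in SAP 5.11 leave out the clinical endpoint's own baseline, so a marker that only tracks severity at entry can look like a predictor of change

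*SAP*

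**What the plan says.** SAP 5.11 specifies the association models in two steps: "The model will include the below clinical endpoint as the dependent variable, with randomization stratification factors", followed by the log10 "baseline biomarker value, treatment group, and treatment by baseline biomarker interaction as the predictor variables". Nothing follows that list. There are five dependent variables. Four are absolute changes to week 24 (DSQ, EREFS, EoEHSS grade and EoEHSS stage); the fifth is "Percent change in peak esophageal intraepithelial eosinophil count (eos/hpf) from baseline to week 24". The output is meant to be read inferentially: "Model coefficients and P-value will be provided to indicate significance of the correlation/association".

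Elsewhere the SAP does adjust for baseline. The co-primary DSQ analysis in SAP 5.6.1 is an ANCOVA with "treatment group, randomization stratification factors, and relevant baseline measurement as covariates included in the model". SAP 5.6.2 carries that approach over to the continuous secondary endpoints, which include the other four outcomes used here. In SAP 5.11 itself, the preceding model, with the biomarker as the outcome, is fitted "with treatment group and randomization stratification factors as fixed factors, and the relevant baseline value as a covariate".

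Protocol 8.2.6 lists among the reasons for collecting these markers "baseline predictors of response and dupilumab mechanism of action".

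**The concern.** Change from baseline usually depends on where the patient started. Protocol 6.2.1 selects on severity: baseline DSQ of at least 10, at least 4 dysphagia episodes in two weeks, and at least 15 eos/hpf in two of three regions. Thresholds of this kind produce regression to the mean. DSQ and EREFS also stop at 0, so milder patients have less room to improve.

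The protocol presents the markers as connected with EoE pathophysiology and type 2 inflammation. Some correlation with baseline severity is therefore plausible, though the documents do not show it.

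If both links exist, a model without the endpoint's baseline assigns part of the severity effect to the biomarker. A marker that says only how ill the patient was at entry could then be reported as associated with change, in an analysis whose purpose includes finding baseline predictors of response. Leaving out a prognostic covariate also inflates the residual variance, which costs precision in every term, including the treatment-by-biomarker interaction.

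**Working it through.** The documents give no power, sample size or error rate for these models, so there is no stated figure to reproduce. The check asks how often the planned model flags a marker that has no relation to change once baseline severity is known.

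**Inputs from the documents.** 210 patients, 70 in each of three arms (SAP 2.1); SD of DSQ change 15.0 (SAP 2.3); predictor list from SAP 5.11; nominal two-sided 0.05.

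**Assumptions, not in the documents.** r, the correlation of marker with endpoint baseline, 0.2 to 0.4; rho, the correlation of endpoint baseline with change, -0.4 to -0.6.

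**Step 1: induced correlation.** If the marker acts only through baseline, its correlation with change is r × rho. In absolute value this runs from 0.2 × 0.4 = 0.08 to 0.4 × 0.6 = 0.24.

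**Step 2: single biomarker coefficient.** With treatment-by-biomarker terms and reference coding (the SAP states no coding), this coefficient is the slope in one arm of 70. By the Fisher approximation, z = atanh(|r × rho|) × √(n − 3):
- 0.08: 0.0802 × √67 = 0.66, rejection about 10%.
- 0.24: 0.2448 × √67 = 2.00, rejection about 52%.

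Simulation of the SAP model gives 10% to 51%. With the endpoint's baseline added it gives 4% to 7%, that is, about 5%.

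**Step 3: slope averaged over the arms.** This uses all 210 patients, so the same induced correlation is easier to detect. These runs assumed a DSQ baseline SD of 12 and slopes of change on baseline of -0.3, -0.5 and -0.7. The corresponding rho is slope × 12/15, that is -0.24, -0.40 and -0.56.

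| Marker–baseline correlation | Slope -0.3 | Slope -0.5 | Slope -0.7 |
|---|---|---|---|
| 0.1 | 7% | 9% | 13% |
| 0.2 | 10% | 21% | 36% |
| 0.3 | 18% | 39% | 67% |
| 0.5 | 39% | 81% | 99% |

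With the endpoint's baseline added, every cell returns to between 4.4% and 5.9%. If either link is zero, the planned model also stays near 5%.

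**Step 4: treatment-by-biomarker interaction.** With one slope of change on baseline in all arms, the interaction test rejects in about 5% of trials with or without the baseline. With a slope of -0.3 on placebo and -0.7 on both dupilumab arms:

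| Model | r = 0.3 | r = 0.5 |
|---|---|---|
| As in SAP 5.11 | 9.6% | 15.2% |
| Plus endpoint baseline | 9.2% | 16.6% |
| Plus treatment-by-endpoint-baseline as well | 5.0% | 4.0% |

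The baseline main effect alone therefore does not repair the interaction test when slopes differ by arm.

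**Step 5: precision.** Baseline explains rho² of the within-arm variance of change: 0.4² = 16% to 0.6² = 36%. That part of the residual variance is removed when the covariate enters.

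**The case against.** The strongest reply is that SAP 5.11 sets out to explore correlation. A marker that tracks severity, when severity predicts change, has a real unadjusted correlation with change. On that view the unadjusted model answers a legitimate question, and the rejections above are false positives only against a conditional null that the SAP never states. This stands as a reason to allow the unadjusted coefficients to be reported. It does not justify reporting only those, because the protocol's stated interest is in predictors of response, and a marker that repeats the baseline score adds nothing to it.

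Several stronger readings are tempting, and the documents do not support them:

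- **That a severity-tracking marker is bound to appear predictive.** This needs two correlations of at least moderate size, and the documents give neither.
- **That the error rate reaches 15% to 85%.** Those figures come from a joint test of the biomarker and its interactions under the same assumptions. SAP 5.11 specifies no joint test.
- **That prediction of dupilumab response is generally biased.** That question rests on the interaction, which stays near 5% unless slopes differ by arm.
- **That all five endpoints suffer equally.** Percent change in eosinophils is already scaled to baseline. If reductions are roughly proportional, the bias may be small.
- **That the logistic model for histologic response departs from the SAP's own practice by omitting baseline eosinophil count.** The CMH analysis of that response in SAP 5.6.1 adjusts only for age group and PPI use, so the consistency argument does not carry over.
- **That the log10 wording in the logistic model is a substantive error for "positivity to at least one antigen-specific IgE".** The wording is loose, but it reads naturally as covering the measured values only. The point is editorial.

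**Conclusion.** The omission is real. The predictor list is closed, nothing elsewhere in the SAP or protocol adds the endpoint's baseline, and calling the model an ANCOVA does not supply it, because the biomarker is already the continuous covariate. The biomarker slope can therefore be significant merely because the marker tracks severity.

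The size depends on the assumed correlations. It also rests on a full 70 per arm; SAP 5.11 uses observed data, so the actual numbers, and with them the rejection rates, would be somewhat lower.

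The consequences are limited. The models are exploratory and lie outside the testing hierarchy in SAP 5.6.3, so no primary or secondary conclusion is touched. The point is a free improvement, not a defect in the confirmatory analysis.

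**What to change.** In SAP 5.11, add the baseline value of the clinical endpoint as a covariate to each ANCOVA relating a baseline biomarker to change or percent change. Specify a sensitivity model that also includes treatment-by-endpoint-baseline, and read the treatment-by-biomarker interaction alongside it. The unadjusted coefficients may be reported next to the adjusted ones, labelled as such.

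While the section is open, one clause can state that the log10 transformation applies to measured values and not to IgE positivity.

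The cost is one covariate per model, and two further interaction terms with three arms in the sensitivity model. All the values are already collected for the efficacy ANCOVAs, so only SAP wording and minor programming change.

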## **5.12. Analysis of Psychometric Validity of Patient Reported Outcome Measures**

The Sponsor will submit evidence of questionnaire measurement properties using Part B data by conducting the analyses described in a separate Psychometric Analysis Plan (PAP).

## 6. DATA CONVENTIONS

The following analysis conventions will be used in the statistical analysis.

### 6.1. Definition of Baseline for Efficacy/Safety Variables

Unless otherwise specified, the study baseline assessment for all measurements will be the latest available valid measurement taken prior to the first administration of study drug. If any randomized patients are not treated, the baseline will be the last value on or prior to the randomization. In addition, Part C baseline is defined as the last available valid measurement taken prior to the first dose of extended treatment in Part C. The baseline of DSQ is defined in Section 6.4.

The following rules specify the determination by both date/time information:

1. For AE, lab (including biomarker), PK and ADA data, both date and time of the measurement will be used to determine baseline by comparing with the first injection date and time.
2. For other data except AE, lab (including biomarker), PK or ADA, only date of the measurement will be used to determine baseline by comparing with the first injection date.

For re-screened patients, all data from the same patient will be used to derive baseline regardless of whether the data are from the screen failure subject ID or enrolled subject ID.

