10.5. Additional Statistical Data Handling Conventions

The following analysis and data conventions will be followed:

Definition of baseline:

- The baseline assessment for each study part will be the latest, valid predose assessment available for the corresponding study part, respectively

General rules for handling missing data:

- If the start date of an AE or concomitant medication is incomplete or missing, it will be assumed to have occurred on or after the intake of study medication, except if an incomplete date (eg, month and year) clearly indicates that the event started prior to treatment. If the partial date indicates the same month or year of the intake of study medication date, then the start date by the study medication intake date will be imputed; otherwise, the missing day or month by the first day or the first month will be imputed.
- No imputations for missing laboratory data, ECG data, vital sign data, or physical examination data will be made.

Unscheduled assessments:

- Extra assessments (laboratory data or vital signs associated with non-protocol clinical visits or obtained in the course of investigating or managing AEs) will be included in listings and summaries. If more than 1 laboratory value is available for a given visit, the first observation will be used in summaries and all observations will be presented in listings.

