#### **4.5.3. Vital Signs**

Vital signs, including heart rate, blood pressure, respiration rate, and body temperature will be collected predose and 30 minutes post-dose at the initial screening visit (visit 1), every scheduled visit and the unscheduled visit before rescue treatment. Heart rate and blood pressure will be measured with the patient in a sitting position, after the patient has rested comfortably for at least 5 minutes. Weight is measured at the initial screening visit (visit 1), every scheduled visit (except week 1, week 40, week 44, and week 48 visits). Height is measured at the initial screening visit (visit 1), week 24, and week 52 (EOS) or ET visits.

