**Table 2: Analysis Visit Window for Safety and Biomarkers in Part B**

Visit from SOE	Target Study Day in Part B a	Analysis Window based on Study Day in Part B					
		Vital signs	Weight	Physical examination, ECG, Height	Laboratory, PK, ADA	Eotaxin-3, Total IgE, Allergen-specific IgE, IgG4	TARC
Baseline	1	≤1	≤1	≤1	≤1	≤1	≤1
Week 1	8	[2, 11]					
Week 2	15	[12, 22]	[2, 22]				
Week 4	29	[23, 43]	[23, 43]			[2, 57]	[2, 89]
Week 8	57	[44, 71]	[44, 71]				
Week 12	85	[72, 99]	[72, 99]		[2, 113]	[58, 127]	
Week 16	113	[100, 127]	[100, 127]				
Week 20	141	[128, 155]	[128, 155]		[114, 155]		
Week 24 (Part B end of treatment)	169	[156, 190] Error! Reference source not found.	[156, 190] Error! Reference source not found.	[2, 190] Error! Reference source not found.	[156, 190] Error! Reference source not found.	[128, 190] Error! Reference source not found.	[90, 190] Error! Reference source not found.
Week 28 c (Extended period of Part B)	197	[191, 204]					
Week 30 c (Extended period of Part B)	211	[205, 218]					
Week 32 c (Extended period of Part B)	225	[219, 232]					
Week 34 c (Extended period of Part B)	239	[233, 246]					
Week 36 c (Extended period of Part B)	253	≥247					

a **Error! Reference source not found.** Study days are calculated from the day of 1st injection of Part B. Study day = (date of assessment – 1st injection date +1) when date of assessment ≥ 1st injection date; otherwise study day = (date of assessment – 1st injection date). If patient never received any dose of study drug, randomization date will be used in place of 1st injection date.

b **Error! Reference source not found.** If unscheduled or ET visit occurs in this window and it is after the first dose of Part C, it will be considered for Week 26.

c Those are dummy analysis visits windows for patients with extended dosing in Part B. ET or unscheduled visit occurred after week 24 visit and before first dose of part C will be mapped per Table 5.

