  - a. If COVID-19 restrictions limit the availability of staff or the patient to have in-clinic visits, procedures/sample collection should occur at the next available in-clinic visit. Pregnancy testing must be performed as indicated (in-clinic or at-home) monthly (at a minimum) and results reported in a timely manner.
8. DSQ eDiary will be completed once daily by the patients after their last meal of the day but before they go to bed. Site personnel should conduct regular checks of patient eDiary compliance.
9. Patient Global Impression of Change (PGIC) of Dysphagia and Patient Global Impression of Severity (PGIS) of Dysphagia will be completed by the patient via electronic questionnaire at the indicated site visits.
10. EoE Impact Questionnaire and EoE Symptom Questionnaire will be completed by the patient via electronic questionnaire at the indicated site visits.
11. Total Nasal Symptom Score (TNSS) and Rhinoconjunctivitis Quality of Life Questionnaire for patients aged 12+ years [RQLQ(S)+12] will be administered only to patients with a documented history of allergic rhinitis; Asthma Control Questionnaire-5 (ACQ-5) will be administered only to patients with a documented history of asthma; Patient-Oriented Eczema Measure (POEM) will be administered only to patients with a documented history of AD. TNSS, POEM, ACQ-5 and RQLQ(S)+12 will be completed via electronic questionnaire and at the indicated site visits. The questionnaires will be administered only to the subset of patients who fluently speak the language in which the questionnaire is presented (based on the availability of validated translations in participating countries).

12. EoE-EREFS should be completed by the investigator before biopsies for all patients are performed. For Part B enrolled patients, EoE-EREFS will be performed by both the investigators who perform the endoscopies as well as a centralized reading center, that will provide EoE-EREFS analysis and scoring from endoscopy imaging. For all endoscopies, the investigators will assess minor esophageal features including mucosal inflammatory and remodeling features.
13. At visits 3 through 6, vital signs (body temperature, blood pressure, respiratory rate, heart rate) should be taken predose and 30 minutes ( $\pm 10$  minutes) post-dose. Vital signs should be taken predose at all other indicated visits.

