9. EoE-EREFS should be completed by the investigator before biopsies for all patients are performed. For Part B enrolled patients, EoE-EREFS will be performed by both the investigators who perform the endoscopies as well as a centralized reading center who will provide EoE-EREFS analysis and scoring from endoscopy imaging. For all endoscopies, the investigators will assess minor esophageal features including mucosal inflammatory and remodeling features.
10. Endoscopy/EoE-EREFS/biopsy procedures should be performed after all other efficacy and safety assessments. The EndoFLIP procedure to measure esophageal distensibility may

be performed during the esophagogastroscope procedures at selected North American sites in approximately 150 adult patients.

Note: All randomized patients found to have stomach and/or duodenal abnormalities at baseline will have follow-up stomach and/or duodenal biopsies at weeks 24 and 52.

- a. For patients who receive rescue treatment, endoscopy/EoE-EREFS/biopsy procedures will be performed prior to initiation of rescue treatment. Patients undergoing endoscopy/biopsy prior to rescue will not undergo the scheduled endoscopy/biopsy at weeks 24 and 52.
11. At visits 11 and 12, vital signs (body temperature, blood pressure, respiratory rate, heart rate) should be taken predose and 30 minutes ( $\pm 10$  minutes) post-dose. Only predose vital signs are required at subsequent visits.
12. For adolescents only
13. In case of a positive urine pregnancy test, the study treatment will be withheld and a serum pregnancy test to confirm the pregnancy should be performed as soon as possible. A confirmed pregnancy will lead to study drug discontinuation in all cases.
14. If COVID-19 restrictions limit the availability of staff or the patient to have in-clinic visits, the clinic staff should make every effort to contact the patient at the timepoint of the expected in-clinic visit to collect any AEs (including ISRs), any change in concomitant medications and/or procedures, and monthly pregnancy test results, if required.

Footnotes for Table 3

1. Patients who are withdrawn from study drug will be asked to complete the 12-week follow-up period and the end of study visit.
2. DSQ eDiary will be completed once daily by the patients after their last meal of the day but before they go to bed. Site personnel should conduct regular checks of patient eDiary compliance.

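### The SAP's date-only rule for the vital-sign baseline cannot separate the predose from the 30-minute post-dose reading on the first-dose day

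*SAP*

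**What the plan says.** **Definition.** SAP 6.1 opens with the principle that "the study baseline assessment for all measurements will be the latest available valid measurement taken prior to the first administration of study drug", and gives the matching definition for Part C. SAP 5.7 repeats it for safety summaries and for Part C PCSVs. Protocol 10.5 agrees: "The baseline assessment for each study part will be the latest, valid predose assessment available for the corresponding study part".

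**Operating rules.** SAP 6.1 then gives two rules for deciding which values qualify. Rule 1, for adverse event, laboratory, PK and ADA data, is time-based: "both date and time of the measurement will be used to determine baseline by comparing with the first injection date and time". Rule 2 covers everything else: "For other data except AE, lab (including biomarker), PK or ADA, only date of the measurement will be used to determine baseline". Vital signs are not in the rule 1 list, so rule 2 applies to them.

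**Schedule.** In SAP 11.2, footnote 13 to the Part B schedule says: "At visits 3 through 6, vital signs (body temperature, blood pressure, respiratory rate, heart rate) should be taken predose and 30 minutes" after dosing. Footnote 11 to the Part C schedule says: "At visits 11 and 12, vital signs (body temperature, blood pressure, respiratory rate, heart rate) should be taken predose and 30 minutes" after dosing. Visit 3 is the day of the first Part B dose and visit 11 the day of the first Part C dose.

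**Windows.** SAP 6.4, Tables 2 and 4, put the vital-sign baseline at study day 1 or earlier and open the next vital-sign window on day 2. Day 1 is the date of the first injection in the part concerned.

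**The concern.** On each first-dose day, two vital-sign readings with the same date lie on opposite sides of the injection. A rule that looks only at the date cannot tell which one came before dosing, so it cannot deliver the baseline that the same section defines. The time-based rule is also missing where it is most needed. Laboratory, PK and ADA samples are collected predose by design and still get date and time. Vital signs have a planned post-dose reading on the key day and do not.

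At stake is the objective record of the first-dose response. Systemic hypersensitivity is the important identified risk in Protocol 3.2.3.2, and both it and anaphylactic reactions are adverse events of special interest (AESIs). The PCSV limits in SAP 11.3 for heart rate, blood pressure and respiratory rate refer to the baseline value. A wrong baseline therefore affects the first-dose reading and every later comparison in that part. For Part B placebo patients, visit 11 is the first planned exposure to dupilumab.

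**Working it through.** The plan states no figure on this point, so there is none to reproduce. The check has two steps.

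**1. What rule 2 can select**

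- *Same-day values qualify* (date on or before the first injection date). This fits the day-1-or-earlier windows in Tables 2 and 4. Both visit 3 readings qualify, and the latest of them is the post-dose one if time is used to rank them. If time is not used, the choice is undefined.
- *Same-day values do not qualify* (date strictly before). Both visit 3 readings drop out. The previous scheduled vital signs are at visit 2, day -21 ± 7, so baseline is about 21 days old. In Part C the previous scheduled reading is at visit 10: day 169 − day 141 = 28 days earlier.

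Neither interpretation reliably gives the Day 1 predose value. No other rule fills the gap. The same-day tie-break in SAP 6.4 concerns unscheduled visits, and the first-observation rule in Protocol 10.5 concerns laboratory values. Nothing says that a nominal predose label will be used.

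**2. What follows for the tables**

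Inputs are the adult limits in SAP 11.3. Low systolic pressure is ≤95 mmHg with a fall of ≥20. High heart rate is ≥120 bpm with a rise of ≥20. The patient values below are assumed for illustration and are not from the documents.

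- Systolic pressure: visit 2 = 122; Day 1 predose = 120; Day 1 post-dose = 88; Week 1 = 118; Week 4 = 94.
- Heart rate: visit 2 = 76; Day 1 predose = 75; Day 1 post-dose = 125; Week 1 = 74; Week 4 = 122.

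Change = value − baseline. A value is flagged when both the level and the change limits are met.

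| Baseline used | Variable | Day 1 post-dose | Week 1 | Week 4 |
|---|---|---|---|---|
| Day 1 predose | SBP (120) | 88 − 120 = −32, flagged | 118 − 120 = −2 | 94 − 120 = −26, flagged |
| | HR (75) | 125 − 75 = +50, flagged | 74 − 75 = −1 | 122 − 75 = +47, flagged |
| Day 1 post-dose | SBP (88) | 0, not flagged | 118 − 88 = +30 | 94 − 88 = +6, not flagged |
| | HR (125) | 0, not flagged | 74 − 125 = −51 | 122 − 125 = −3, not flagged |
| Visit 2 | SBP (122) | 88 − 122 = −34, flagged | 118 − 122 = −4 | 94 − 122 = −28, flagged |
| | HR (76) | 125 − 76 = +49, flagged | 74 − 76 = −2 | 122 − 76 = +46, flagged |

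The Week 1 values are not flagged under any baseline because they do not meet the level limits. With the post-dose baseline they nevertheless show large changes that are artefacts. In this example, masking occurs only with the post-dose baseline. With the visit 2 baseline the flags are kept, but the reference is not the latest predose value.

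**The case against.** The best defence is that the principle governs. SAP 6.1, SAP 5.7 and Protocol 10.5 all require a value before dosing, a post-dose reading violates all three, and nothing says that rule 2 overrides them. SAP wording that admits values on the date of the first dose appears only in the Part C efficacy text of 5.6.2. Ranking two same-day readings already needs the time or a label, and a programmer who has either could simply pick the predose one. This stands as a reason not to treat the post-dose reading as the certain baseline. It does not remove the conflict, because rule 2 is the stated way to apply the principle and excludes the one piece of information needed.

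A second defence concerns Tables 2 and 4. SAP 6.4 applies the windows when scheduled-visit data are unavailable, and the visit 3 and visit 11 readings are scheduled data. SAP 5.7 also runs detection from the first injection to the end of study, so the Day 1 post-dose reading lies inside it. Both points are right: the windows are consistent with the same-day interpretation but do not compel it. Being inside the detection interval does not help, however, if the same reading also serves as baseline.

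A reader might also infer that an immediate first-dose reaction would go unseen. The documents do not support that. Adverse events are assessed 30 minutes after dosing at visits 3 to 6 and at visit 11 (visit 12 if possible). All events with onset in the treatment period count as treatment-emergent, and adverse event data use date and time. Anaphylactic and systemic hypersensitivity reactions are AESIs with their own search criteria in SAP 11.4. Protocol 9.4.5 also makes an abnormal vital sign with symptoms, or one needing intervention, reportable as an adverse event.

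**Conclusion.** The point holds as a conflict inside the SAP: a stated rule cannot produce the baseline that the SAP and protocol define. It does not show that the post-dose reading will be used. That is one possible outcome, and the visit 2 value is the other.

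The rule potentially affects every treated Part B patient with both Day 1 readings, at most about 210 as planned, and every Part C entrant at visit 11. These are patients exposed to the ambiguity, not missed events. The documents give no frequency of post-dose threshold crossings, and the numerical examples are illustrative.

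The effect is limited to the vital-sign PCSV and change-from-baseline summaries. What could be lost is objective evidence of first-dose changes, mainly those not reported as adverse events. No efficacy endpoint, alpha level or power figure is touched. The correction should be made before the analysis is programmed.

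**What to change.** In SAP 6.1, either move vital signs to rule 1, so that date and time are compared with the first injection in each part, or name the nominal predose reading on the first-dose date of each part as baseline. State that the 30-minute reading on that day is a post-baseline value. Give it its own time point in Tables 2 and 4, and say that it counts for PCSV detection and the change-from-baseline summary. Align 6.1, 5.7 and the two tables, so that the day-1-or-earlier window cannot be taken to include a post-dose vital sign.

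The cost is a sentence or two in 6.1 and one row in each table. Both readings are already scheduled, so no new assessment is needed. This assumes that the database records either the time of measurement or a predose/post-dose label, which should be confirmed because the documents do not say.
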